Results of the phase 3 program demonstrated that, relative to placebo, the TAK-491 20, 40, and 80 mg doses produce clinically and statistically significant reductions in systolic blood pressure (SBP) and diastolic blood pressure (DBP), as assessed by both ambulatory blood pressure monitoring (ABPM) and clinic blood pressure measurements. The differences between doses were greater for subgroups of subjects characterized by more severe and/or resistant hypertension, including black subjects, subjects with renal impairment, and subjects with Grade 2 hypertension. In each study, most of the blood pressure-lowering effect of TAK-491 was observed within 2 weeks of treatment; a plateau of effect was generally reached by week 4 and reductions were maintained through week 6 in short-term studies and over the long-term in two 6-month studies (and up to 1 year in open-label studies). In replicate studies, TAK-491 at 80 mg was shown to reduce systolic blood pressure more effectively than olmesartan medoxomil 40 mg and valsartan 320 mg, the highest approved doses in the US.

In two controlled studies, coadministration of TAK-491 with chlorthalidone (491-009) and amlodipine (491-010) provided additional blood pressure reduction compared with chlorthalidone or amlodipine monotherapy. In open-label studies, addition of diuretic therapy to treatment with TAK-491 led to additional blood pressure reductions in subjects who did not reach blood pressure targets after initiation of TAK-491.

In clinical trials with hypertensive subjects, treatment with TAK-491 was well-tolerated with an overall incidence of adverse reactions and withdrawals due to adverse events similar to that of placebo. Generally, adverse reactions were mild, not dose related and similar regardless of age, gender and race. The safety and tolerability profile of TAK-491 was similar to that of other agents of the ARB class. Commonly reported adverse events included headache, dizziness, urinary tract infection (UTI), nasopharyngitis and dyslipidemia; diarrhea was reported more frequently with TAK-491 than placebo. As compared with other ARBs, a higher incidence of mechanism-based

side effects of dizziness and reversible serum creatinine elevations were observed with TAK-491, which is consistent with the greater antihypertensive effect of the drug.

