6.2 Justification for Study Design, Dose, and Endpoints

TAK-491 is a prodrug that is rapidly hydrolyzed to the active moiety, TAK-536, which is a long-acting, angiotensin II AT1 receptor blocker (ARB). TAK-491 has been shown to have a strong antihypertensive effect, predictable pharmacokinetic and metabolic profiles, a prolonged duration of action, and good safety and tolerability profiles when administered as a monotherapy to hypertensive subjects. The phase 3 TAK-491 studies have shown that TAK-491 80 mg reduced blood pressure more effectively than olmesartan medoxomil 40 mg and valsartan 320 mg, the highest approved doses in the US. As of February 2016, TAK-491 has been approved for the treatment of hypertension, either alone or in combination with other antihypertensive agents, in a total of 59 countries worldwide, including approval in the United States by the Food and Drug Administration (FDA) in February 2011 and in the European Union by the European Medicines Agency (EMA) in December 2011.

The objective of this phase 3, randomized, double-blind, parallel-group study of 8 weeks duration is to examine the efficacy and safety of TAK-491 compared to valsartan in Chinese subjects with mild to moderate essential hypertension. Since the intended registration doses for TAK-491 in China will be 40 mg and 80 mg, these were the TAK-491 doses selected for this study. Valsartan is a marketed, widely used ARB with known efficacy in mild to moderate essential hypertension and the highest approved dose in China is 160 mg, with 320 mg as the highest approved dose in other regions (United States, European Union, etc). In addition in Takeda's global studies (TAK-491-019 and 301), TAK-491 40 mg and 80 mg were evaluated in comparison with 320 mg of valsartan. Based on these considerations, and to reflect standard of care practices in China, 40 mg and 80 mg TAK-491 were selected for comparison with 160 mg of valsartan in this study.

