13.1.3 Efficacy Analysis

Unless otherwise specified, efficacy analyses will be performed using the FAS and all statistical inference will use a 2-sided 0.05 significance level. A subject will be included in the primary analyses only when there is both a baseline value and at least 1 value during the double-blind treatment period. Missing values will be imputed using last observation carried forward (LOCF) methodology. In the LOCF analysis data set, the last post-baseline double-blind observed value is **CONFIDENTIAL**

carried forward and used for all subsequent scheduled time points where data are missing (eg, the subject has missing data or has dropped out of the study).

The primary analysis will be based on an analysis of covariance (ANCOVA) model for change in clinic SBP from baseline to week 8. The model will include treatment as a fixed effect and baseline clinic SBP as a covariate. From the framework of the ANCOVA the following will be determined: treatment LS mean, LS mean for the difference between TAK-491 and valsartan, p-value and 2-sided 95% confidence intervals for the treatment difference. For the primary analysis the overall type 1 error rate of 0.05 will be controlled using the 4 step sequential test described below.

- Step 1: A test for noninferiority of TAK-491 80 mg to valsartan 160 mg will be performed using a noninferiority margin of 1.5 mm Hg. If the upper limit of the 2-sided 95% CI of the treatment difference (TAK-491 valsartan) is not greater than 1.5 then proceed to Step 2.
- Step 2: A test for noninferiority of TAK-491 40 mg to valsartan 160 mg will be performed using a noninferiority margin of 1.5 mm Hg. If the upper limit of the 2-sided 95% CI of the treatment difference (TAK-491 valsartan) is not greater than 1.5 then proceed to Step 3.
- Step 3: A test for significant difference between TAK-491 80 mg versus valsartan 160 mg will be performed at the 5% level. If the p-value is not greater than 0.05 then proceed to Step 4.
- Step 4: A test for significant difference between TAK-491 40 mg versus valsartan 160 mg will be performed at the 5% level.

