13.3 Determination of Sample Size

Assuming an SD of 17 mm Hg and a 10% dropout rate, a sample size of 200 subjects per treatment group (total of 600 subjects) is sufficient to achieve at least 90% power to detect a difference of 6 mm Hg between TAK-491 dose and valsartan by a 2-sample t-test on the mean change from baseline to Week 8 in mean sitting clinic SBP at 0.05 2-sided significance level. This sample size will also provide, for the above assumptions, at least 90% power for demonstrating noninferiority with a margin of 1.5 mm Hg between TAK-491 and valsartan.

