#### 3.0 INTRODUCTION

This statistical analysis plan (SAP) describes the planned statistical analyses and data presentations for TAK-391\_305, a phase 3, double-blind, randomized, parallel-group study to evaluate the efficacy and safety of TAK-491 compared with valsartan over an 8 week treatment period in Chinese subjects with essential hypertension (mean sitting clinic systolic blood pressure (SBP)  $\geq$  150 and  $\leq$  180 mm Hg on Day 1).

The purpose of this document is to ensure the credibility of the study findings by specifying the statistical approaches to the analysis of the double-blind data prior to database lock. This SAP was developed based on the International Conference on Harmonization (ICH) E3 and E9 Guidelines and in reference to the following document:

• Protocol TAK-491\_305 Amendment No.4 dated 09 May 2016.

Any deviations during the analysis and reporting process from the current SAP will be described and justified in the final report. Analysis issues that suggest changes to the principal features stated in the protocol will be documented in a protocol amendment. Otherwise, the statistical analysis plan will be updated through an amendment with the changes in the analysis documented in the amendment.

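### Does placing 80 mg superiority behind 40 mg noninferiority undermine the trial's planned power?

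*Protocol*

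**What the plan says.** The order is 80 mg noninferiority, 40 mg noninferiority, 80 mg superiority, 40 mg superiority. It appears identically in the Protocol synopsis (2.0), Protocol 13.1.3 and SAP 7.9.1. Noninferiority uses a 1.5 mm Hg margin and the upper limit of a 2-sided 95% confidence interval. The move from Step 2 to Step 3 requires that the 40 mg limit "is not greater than 1.5 then proceed to Step 3". Then follows "Step 3: A test for significant difference between TAK-491 80 mg versus valsartan 160 mg will be performed at the 5% level".

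Protocol 13.3 and SAP 6.0 size the trial at 200 per arm, with SD 17 mm Hg and 10% dropout, for "at least 90% power to detect a difference of 6 mm Hg between TAK-491 dose and valsartan by a 2-sample t-test". They claim at least 90% power for noninferiority under the same assumptions. One effect serves both doses. Neither section gives a separate 40 mg effect or a power for the sequence as a whole.

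**The concern.** Step 2 is called noninferiority, but with this margin and sample size it is a demanding test. 40 mg has to be observed about 2 mm Hg better than valsartan to pass, and a 40 mg dose truly equal to valsartan passes only about 13% of the time. So the chance of confirming 80 mg superiority, the kind of comparison that sized the trial, depends on how another dose performs.

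The background gives some reason to expect the doses to differ. Protocol 4.3 says "The differences between doses were greater for subgroups of subjects characterized by more severe and/or resistant hypertension", and this trial enrols SBP from 150 to 180 mm Hg. Protocol 6.2 says of the earlier studies that "TAK-491 40 mg and 80 mg were evaluated in comparison with 320 mg of valsartan", whereas 4.3 reports only that "TAK-491 at 80 mg was shown to reduce systolic blood pressure more effectively than olmesartan medoxomil 40 mg and valsartan 320 mg". If 40 mg missed Step 2, the 80 mg superiority p-value would have no confirmatory standing, and that could not be repaired after unblinding.

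**Working it through.** **Inputs.** SD 17, 200 randomized per arm, 10% dropout (hence 180) and effect 6 mm Hg come from Protocol 13.3 and SAP 6.0. Margin 1.5 and 2-sided 0.05 come from Protocol 13.1.3. Allocation is 1:1:1 (Protocol 6.1), so the two contrasts share the valsartan arm and correlate at 0.5.

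**1. The plan's own figures.** SE = 17 × √(2/180) = 1.792.
- Superiority: Φ(6/1.792 − 1.960) = Φ(1.388) = 91.7%.
- Noninferiority with a true benefit of 6: Φ(7.5/1.792 − 1.960) = Φ(2.225) = 98.7%.
- With all 200 analysed, SE = 1.700 and superiority power is 94.2%.

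Both statements of at least 90% reproduce.

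**2. How hard Step 2 is.** The half-width is 1.960 × 1.792 = 3.51, so 40 mg must be observed at least 3.51 − 1.5 = 2.01 mm Hg better. At 200 per arm this is 3.33 − 1.5 = 1.83.

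**3. Power of Step 3 within the sequence.** Success at Step 3 implies success at Step 1. The probability is therefore the bivariate normal Φ₂(6/SE − 1.960, (1.5 + d)/SE − 1.960; 0.5), where d is the true 40 mg advantage and 80 mg is fixed at 6. Every value of d except 6 is an assumption.

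| d (mm Hg) | 0 | 2 | 3 | 4 | 5 | 6 | 80 mg test alone |
|---|---|---|---|---|---|---|---|
| n = 180 | 13.0% | 48.5% | 68.1% | 81.8% | 88.6% | 91.0% | 91.7% |
| n = 200 | 14.0% | 53.0% | 73.3% | 86.3% | 92.0% | 93.8% | 94.2% |

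At the plan's stated effect for both doses the gate costs 91.7 − 91.0 = 0.7 points at n = 180, and Step 3 still exceeds 90%.

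**4. Type 1 error.** Each step is tested at 2-sided 0.05, and only after every earlier step has succeeded. A false claim first requires rejection of the earliest true null in the order, so familywise error stays within 0.05 without adjustment.

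**5. The alternative.** After Step 1, one could test 40 mg noninferiority and 80 mg superiority in parallel at 0.025 each, and retest the other at 0.05 if either succeeds. Simulated results at n = 180 (simulation error about 0.1 to 0.2 points):

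| True advantage, 80 mg / 40 mg | 40 mg noninferiority, fixed order → parallel | Change in 80 mg superiority |
|---|---|---|
| 6 / 6 | 97.5% → 97.0% | +0.4 (91.0% → 91.4%) |
| 6 / 4 | 85.9% → 84.3% | +8.0 (81.5% → 89.5%) |
| 6 / 3 | 70.4% → 68.9% | +20.4 (67.8% → 88.2%) |
| 4 / 4 | 78.0% → 74.6% | +1.6 |
| 4 / 3 | 65.5% → 60.9% | +6.1 |
| 3 / 3 | 56.6% → 51.8% | +1.8 |

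The cost to 40 mg noninferiority stays below 2 points only while 80 mg is held at 6. With 80 mg at 3 or 4 mm Hg, the cost is 78.0 − 74.6 = 3.4 to 56.6 − 51.8 = 4.8 points. Where the doses perform alike at those levels, the loss is larger than the gain in 80 mg superiority.

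**The case for a change.** The best case for changing the order is the 6 / 3 row: 20 points of 80 mg superiority for 1.5 points of 40 mg noninferiority, with no change to sample size, margin, endpoint or model. A weaker lower dose is pharmacologically ordinary. The change is cheap before unblinding, since SAP 3.0 already provides that "Analysis issues that suggest changes to the principal features stated in the protocol will be documented in a protocol amendment". All of that stands as arithmetic, and a sponsor who expected a large gap between the doses might well prefer the parallel rule.

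It does not make the present order wrong, for three reasons.

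- The size of the gap is not in the documents. The sentence on dose differences gives a direction without a magnitude. The earlier comparator was valsartan 320 mg, while this trial uses 160 mg. The absence of a reported 40 mg result in 4.3 does not show a small 40 mg effect here.
- The registration aim argues for the present order at least as much as against it. Protocol 6.2 begins its dose rationale with "Since the intended registration doses for TAK-491 in China will be 40 mg and 80 mg". A sponsor seeking both doses can reasonably secure noninferiority for both before spending alpha on superiority for either.
- A failed Step 2 removes only the confirmatory status of the 80 mg superiority test. The estimate, 95% confidence interval and p-value still come from the ANCOVA.

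Stating an assumed effect per dose and a power for the sequence in Protocol 13.3 would be informative. It would alter no analysis or result, and its absence contradicts nothing in the plan.

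**Conclusion.** The concern does not hold. Its figures of 68% and 82% against 92% are reproducible at 180 per arm, but they describe a scenario the plan does not assume. Under the stated 6 mm Hg for a TAK-491 dose, Step 3 has 91.0% power with 180 analysed per arm and 93.8% with 200, so the promised 90% is met with the gate in place. The fixed sequence controls type 1 error, and the parallel alternative trades one claim against another: it gains about 0.4 points of 80 mg superiority at the planned effect and costs 40 mg noninferiority 3.4 to 4.8 points when 80 mg is only 3 or 4 mm Hg better.

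This rests on SD 17, equal arms and the plan's common effect for both doses. LOCF retains dropouts who have a post-baseline value, which moves the analysed number towards 200, and baseline adjustment may lower the residual SD. Either would reduce the gate's cost further. If 40 mg were in truth several mm Hg weaker than 80 mg, power for Step 3 would fall as the working shows; that is a known consequence of a legitimate ordering.

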13.1.4 Safety Analysis

Safety and tolerability will be accessed via treatment emergent adverse events, laboratory results, and other safety variables. Unless otherwise specified safety analyses will be performed using the safety analysis set, and presented by treatment group. Results presented by study visit will also include the final visit; where final visit is defined as the last observation (post-baseline) carried forward no later than 7 days after the last dose of study drug.

13.1.4.1 Adverse Events

Adverse events will be coded using MedDRA. Treatment-emergent adverse events (TEAE) will be defined as any AEs, regardless of relationship to study drug, that occur after the first dose of double-blind study drug, no later than 14 days after the last dose of study drug for AEs, and no later than 30 days after the last dose of study drug for SAEs. TEAEs will be tabulated by system organ

class and preferred term. The TEAE summary tables will include count and percent of subjects reporting the event by treatment group. Therefore, if a subject experiences more than 1 episode of a particular AE, the subject will be counted only once for that event. If a subject has more than 1 AE that codes to the same preferred term, the subject will be counted only once for that preferred term. Similarly, if a subject has more than 1 AE within a system organ class, the subject will be counted only once in that system organ class. Adverse events with onset dates on or after the start of treatment and prior to 14 days (onset date – last date of dose \leq 14) after the permanent discontinuation of the study medication, or continuing AEs diagnosed prior to the date of first dose of study medication and getting worse in severity or intensity after receiving study medication will be summarized.

Serious adverse events with onset dates on or after the start of treatment and prior to 30 days (onset date – last date of dose \leq 30) after the last dose of study medication will be summarized. Specific decision will be made for inclusion of SAEs with onset dates 30 days after the final discontinuation of study medication.

TEAEs will also be presented by causality (relationship to study drug) and severity (mild, moderate, severe). Serious TEAEs, TEAEs leading to study drug discontinuation, and TEAEs leading to death will also be summarized using preferred term and system organ class.

13.1.4.2 Laboratory Analysis

Laboratory test variables will be summarized by treatment group and study visit using descriptive statistics for the observed and change from baseline values. Markedly abnormal laboratory values will be determined and listed by treatment group and study visit. The number and percentage of subjects with markedly abnormal laboratory values in each of the laboratory parameters will be presented. Shift tables displaying the change (number of subjects) relative to the normal range from Baseline to each study visit will also be presented by treatment for each laboratory test. Laboratory data collected more than 7 days after the last dose of study medication will be excluded from the summaries but will be listed.

13.1.4.3 Additional Safety Values

13.2 Interim Analysis and Criteria for Early Termination

No interim analysis is planned.

13.3 Determination of Sample Size

Assuming an SD of 17 mm Hg and a 10% dropout rate, a sample size of 200 subjects per treatment group (total of 600 subjects) is sufficient to achieve at least 90% power to detect a difference of 6 mm Hg between TAK-491 dose and valsartan by a 2-sample t-test on the mean change from baseline to Week 8 in mean sitting clinic SBP at 0.05 2-sided significance level. This sample size will also provide, for the above assumptions, at least 90% power for demonstrating noninferiority with a margin of 1.5 mm Hg between TAK-491 and valsartan.

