6.0 STUDY DESIGN AND DESCRIPTION

6.1 Study Design

This is a phase 3, multicenter, randomized, double-blind, parallel-group study to evaluate the efficacy and safety of TAK-491 compared with valsartan over an 8 week treatment period in Chinese subjects with essential hypertension (trough, sitting clinic SBP \geq 150 and \leq 180 mm Hg on Day 1). This study will be conducted in China at approximately 20 to 25 sites and will include approximately 600 randomized subjects.

Before initiation of treatment, all subjects will participate in a 2-week, single-blind, placebo run-in period (Days -14 to -1). Subjects who have not received antihypertensive treatment within 28 days before screening can be entered into the run-in period as soon as all inclusion and exclusion criteria, including laboratory results, have been verified. Subjects taking previous antihypertensive agents will be required to participate in a 3-week washout/placebo run-in period (Days -21 to -1). If the subject's previous antihypertensive treatment includes amlodipine or chlorthalidone, then the washout/placebo run-in must be extended to 4 weeks (Days -28 to -1). Screening (Visit 1) will be scheduled before the washout/run-in period begins so that laboratory test results can be reviewed and subject eligibility can be confirmed before other treatments are stopped or placebo is initiated. At Day -14 (Visit 2), subjects will receive the first dose of single-blind placebo in clinic.

[figure not shown]
At Day 1 (Visit 5), eligible subjects will be randomly assigned to one of the following 3 groups with a 1:1:1 ratio:

- TAK-491 40 mg QD.
- TAK-491 80 mg QD.
- Valsartan 160 mg QD.

Subjects will be given the first dose of randomized study drug in the clinic at Day 1 (Visit 5). The last dose of randomized study drug will be taken the day of Week 8 visit (Visit 9). End of study assessment will be taken at Week 8/Early Termination (Visit 9). All subjects who receive study drug (placebo or double-blind) will be required to have a follow-up telephone call at approximately 14 days after the last dose.

A schematic of the study design is included as Figure 6.a.

V=visit, N/A=not applicable, D=day, HTN=hypertension, Wk=week, ET=Early Termination.

- (a) The Screening Visit should be scheduled before the washout/run-in period begins so that laboratory tests results can be reviewed and subject eligibility can be confirmed before other treatments are stopped or placebo is initiated.

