## 6.0 DETERMINATION OF SAMPLE SIZE

Assuming a standard deviation (SD) of 17 mm Hg and a 10% drop-out rate, a sample size of 200 subjects per treatment group (total of 600 subjects) is sufficient to achieve at least 90% power to detect a difference of 6 mm Hg between TAK-491 dose and valsartan by a 2 sample t-test on the mean change from baseline to Week 8 in mean sitting clinic SBP at 0.05 2-sided significance level. This sample size will also provide, for the above assumptions, at least 90% power for demonstrating non-inferiority with a margin of 1.5 mm Hg between TAK-491 and valsartan.

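### Does the sample size section overstate the power that the four-step test delivers?

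*Protocol*

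**What the plan says.** Protocol section 13.3, repeated in the synopsis and in SAP section 6.0, takes 200 subjects per arm and gives its inputs as follows: "Assuming an SD of 17 mm Hg and a 10% dropout rate". It then claims "at least 90% power to detect a difference of 6 mm Hg between TAK-491 dose and valsartan by a 2-sample t-test", tested "at 0.05 2-sided significance level". The next sentence covers noninferiority: "This sample size will also provide, for the above assumptions, at least 90% power for demonstrating noninferiority with a margin of 1.5 mm Hg". SAP section 6.0 repeats this as "at least 90% power for demonstrating non-inferiority with a margin of 1.5 mm Hg".

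Protocol section 13.1.3 and SAP section 7.9.1 set out the confirmatory order:

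1. Noninferiority of 80 mg.
2. Noninferiority of 40 mg.
3. Superiority of 80 mg.
4. Superiority of 40 mg: "A test for significant difference between TAK-491 40 mg versus valsartan 160 mg will be performed at the 5% level".

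Each step is reached only if the one before it succeeds. Neither document gives power for the sequence, or noninferiority power at a true difference other than 6 mm Hg.

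**The concern.** The power statement describes a stand-alone t-test, while the trial's claims come from a gated sequence. A reader could take 90% as the chance of each dose's superiority claim. For 40 mg the chance is lower, because the 80 mg test must succeed first. Both doses matter, since protocol section 6.2 names 40 mg and 80 mg as the intended registration doses.

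The noninferiority sentence is terse. The clause that opens with the assumptions lists only the SD and the dropout rate; the 6 mm Hg appears afterwards, as the difference to detect. Someone who reads the assumptions as SD and dropout alone might think the trial has 90% power to show noninferiority of two equally effective drugs. It has nothing like that, and a failed noninferiority test would then be weak evidence of inferiority.

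**Working it through.** **Inputs.** From protocol section 13.3: SD 17 mm Hg, 10% dropout, 200 per arm, a 6 mm Hg difference, two-sided 0.05 and a 1.5 mm Hg margin. From section 6.1: 1:1:1 allocation. Evaluable per arm: 200 × 0.90 = 180.

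**The plan's superiority figure.**
- SE = 17 × √(2/180) = 1.792 mm Hg.
- Power = Φ(6/1.792 − 1.960) = Φ(1.388) = 91.7%; by noncentral t, 91.6%.
- Required n for 90% is 169 evaluable per arm; 169/0.90 = 188 randomized, which is below 200.

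**The plan's noninferiority figure, true difference −6.**
- Power = Φ((1.5 + 6)/1.792 − 1.960) = Φ(2.225) = 98.7%.

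Both claims of at least 90% reproduce.

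**Power through the sequence.** Assume both doses are truly 6 mm Hg better. The two comparisons share the valsartan arm, so their estimates have correlation 0.5. A dose whose upper confidence limit is below zero also meets the 1.5 margin, so reaching and passing Step 4 is the same event as both superiority tests succeeding:
- P(Z₈₀ ≤ 1.388 and Z₄₀ ≤ 1.388), correlation 0.5, = 86.0%.
- With 200 evaluable: SE = 1.700, 6/1.700 − 1.960 = 1.569, giving 89.9%.

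A simulation of 2,000,000 trials with pooled-variance t tests gives these cumulative probabilities:

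| Step | 180 per arm | 200 per arm |
|---|---|---|
| 1. Noninferiority, 80 mg | 98.7% | 99.3% |
| 2. Noninferiority, 40 mg | 97.5% | 98.6% |
| 3. Superiority, 80 mg | 90.9% | 93.7% |
| 4. Superiority, 40 mg | 85.9% | 89.8% |

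**What moves Step 4.** It reaches 90% at 201 evaluable per arm. With 180, the same precision needs a residual SD of 17 × √(180/201) = 16.1, a reduction of about 5%. The primary model adjusts for baseline SBP, and the plan does not say whether 17 is before or after that adjustment. The primary analysis also carries the last value forward and keeps anyone with a baseline and one double-blind value, so the analysed number may be nearer 200 than 180.

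**Noninferiority without the full advantage (one dose, 180 per arm).** Power = Φ((1.5 − true difference)/1.792 − 1.960):

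| True difference (mm Hg) | Power |
|---|---|
| 0 | 13.1% |
| −2 | 49.7% |
| −3 | 70.9% |
| −4 | 86.6% |
| −6 | 98.7% |

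Power of 90% needs a true difference of 1.5 − (1.960 + 1.282) × 1.792 = −4.3 mm Hg. The observed estimate must be at or below 1.5 − 1.960 × 1.792 = −2.0 mm Hg. At equality both doses pass in sequence only 4.7% of the time, and 90% power for one dose would take 2,700 evaluable per arm.

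**The case for a change.** The strongest case for a change is that the sequence decides what may be claimed, so power should be quoted on that basis. Even with no loss of subjects, Step 4 stays just under 90%. The order also ties the doses together: Step 3 waits on 40 mg noninferiority. If 80 mg keeps its 6 mm Hg but 40 mg has only 4 or 3, Step 3 falls from 91% to 82% or 68%, and Step 4 to 59% or 38% (180 per arm). Protocol sections 4.3 and 6.2 report superiority over valsartan 320 mg for 80 mg only, so equal effects at both doses are not evidenced there.

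The arithmetic stands, and so does the observation that sequence power is unreported. The charge of misstatement does not. The sentence names one TAK-491 dose, one comparison and a two-sample t-test, and is right about that test. The assumptions that the noninferiority sentence points back to are most naturally read as including the 6 mm Hg in the sentence just before it; on that reading the claim holds with room to spare. The zero, 3 and 4 mm Hg scenarios are not the plan's. It expects an advantage, tests for it at Steps 3 and 4, and cites 80 mg outperforming twice the valsartan dose used here. Carried-forward values could dilute the effect, but protocol section 4.3 says most of the reduction appears within 2 weeks, with a plateau generally by Week 4.

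**Conclusion.** The concern does not call for a change. Both power statements are correct per comparison under the plan's inputs. If both doses are truly 6 mm Hg better, only the last of the four steps falls short of 90%, at about 86% to 90% for 180 to 200 evaluable per arm with SD 17 and no further gain from the baseline covariate. Dependence of noninferiority power on the assumed advantage is real, at about 13% for one dose and about 5% for both in sequence under equality, but the plan's wording carries that condition, if tersely.

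What remains is a wish for extra figures beside correct ones. Supplying them would leave the sample size, margin, test order, analysis and interpretation rules as they are. A statistician who needs power by step can derive it from the stated inputs, as above. Anyone reading a failed noninferiority result should bear in mind that it required an observed advantage of about 2 mm Hg.
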